- 14.1-1: Summary of Subject Disposition
- 14.2-1.1.1: Analysis of AUC of NRS Pain Intensity Scores through 48 hours – Primary Efficacy Analysis Set - Multiple Imputation Results
- 14.2-1.1.2: Sensitivity Analysis of AUC of NRS Pain Intensity Scores through 48 hours – Secondary Efficacy Analysis Set - Multiple Imputation Results
- 14.2-1.1.3: Sensitivity Analysis of AUC of NRS Pain Intensity Scores through 48 hours – Primary Efficacy Analysis Set – Mixed Model Repeated Measures Results
- 14.2-2.1: Analysis of AUC of NRS Pain Intensity Scores through 24 hours - Primary Efficacy Analysis Set - Multiple Imputation Results
- 14.2-2.2: Summary of AUC of NRS Pain Intensity Scores through 24 hours - Primary Efficacy Analysis Set - Analysis of Variance Model Results - Multiple Imputation Results
- 14.2-3.1: Analysis of AUC of NRS Pain Intensity Scores through 72 hours - Primary Efficacy Analysis Set - Multiple Imputation Results
- 14.2-3.2: Summary of AUC of NRS Pain Intensity Scores through 72 hours - Primary Efficacy Analysis Set - Analysis of Variance Model Results - Multiple Imputation Results
- 14.2-5.1: Analysis of Opioid-Free Subjects through 24 hours - Primary Efficacy Analysis Set
- 14.2-5.2: Analysis of Opioid Free Subjects through 48 hours - Primary Efficacy Analysis Set
- 14.2-5.3: Analysis of Opioid Free Subjects through 72 hours - Primary Efficacy Analysis Set
- 14.3-2.2: Summary of Potentially Clinically Meaningful Abnormal Electrocardiogram Results – Central Read - Safety Analysis Set
- 14.3-3.2: Summary of Potentially Clinically Significant Abnormal Vital Signs – Safety Analysis Set
- 14.3-4.1.2: Summary of Incidence of Treatment-Emergent Adverse Events (TEAEs) - Safety Analysis Set
- 14.3-4.2.2: Summary of Incidence of Serious Treatment-Emergent Adverse Events (TEAEs) - Safety Analysis Set

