A mixed model repeated measures analysis will be performed using only the data imputed using wWOCF but not imputing any missing values outside of the rescue medication windows. The MMRM model will have fixed effects for treatment and time. The initial model will be fit with the treatment-by-time interaction. If this interaction is not significant (p-value > 0.05) the final model will include the main effects only. If the interaction is significant (p-value ≤ 0.05) the interaction will be investigated to determine if it is qualitative or quantitative. If the interaction is quantitative, the final model will include the interaction term. If the interaction is qualitative, additional analyses may be required. The treatment effect at 48 hours will be estimated from the final model.

Tipping Point

A tipping point analysis will be performed using similar imputation technique as the primary AUC calculations (see section [7.1.1.1.1](#)) but adding shift values to the imputation until the primary analysis results change direction (SAS pseudo-code below).

```
PROC MI DATA=OUTDATA_STEPB OUT=OUTDATA_TIP;
  BY _IMPUTATION_;
  CLASS TREATMENT;
  MONOTONE REG(T1 = TREATMENT / DETAILS);
  MONOTONE REG(T2 = TREATMENT T1 / DETAILS);
  ...
  MONOTONE REG(T(n-1) = TREATMENT T1 T2 T3 ... T(n-2) / DETAILS);

  MNAR ADJUST(T1 / SHIFT=Q ADJUSTOBS=(TREATMENT='EXPAREL'));
  MNAR ADJUST(T2 / SHIFT=Q ADJUSTOBS=(TREATMENT='EXPAREL'));
  ...
  MNAR ADJUST(T(n-1) / SHIFT=Q ADJUSTOBS=(TREATMENT='EXPAREL'));
  MNAR ADJUST(Tn / SHIFT=Q ADJUSTOBS=(TREATMENT='EXPAREL'));

  VAR TREATMENT T1 T2 T3 ... Tn
RUN;
```

where Q is the value to shift the results.

If the result from the primary efficacy analysis is statistically significant, the above code will be run iteratively for integer values of Q from 1 to 10 analyzing each step of the way until the result “tips” from statistically significant to not statistically significant. If the primary efficacy analysis result is not statistically significant, the above code will be run iteratively for integer values from -1 to -10 until the result “tips” from not clinically significant to clinically significant. The value of Q that results in the change in significance will be reported along with the analysis results.

Original Imputation Method

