 NRS = numeric rating scale at rest, where 0 = no pain and 10 = worst possible pain;
 Summary statistics based on the subject mean AUC from the multiple imputations;
 wWOCF + LOCF = imputation using the worst observation prior to use of rescue medication within a medication window and last-observation-carried-forward for missing values.
 [1] From an ANOVA with main effects of treatment and site.

Source: list SAS datasets used to create table
 SAS X.Y

DDMONYYYYTHH:MM
 program_name

Note to programmer: The raw SAS outputs from the procedures used to produce ALL 14.2-1.1 & 14.2-1.2 series tables should be saved as a possible appendix to the clinical study report (CSR). Use this template for the following tables:

Table 14.2-1.1.2: Sensitivity Analysis of AUC of NRS Pain Intensity Scores through 48 hours - Secondary Efficacy Analysis Set - Multiple Imputation Results

Table 14.2-1.1.3: Sensitivity Analysis of AUC of NRS Pain Intensity Scores through 48 hours - Primary Efficacy Analysis Set - Mixed Model Repeated Measures Results

| Pacira Pharmaceuticals | | (Page X of Y) | | Protocol: 402-C-329 |
|--|--|----------------|----------------|---------------------|
| Table 14.2-1.1.4: Sensitivity Analysis of AUC of NRS Pain Intensity Scores through 48 hours - Primary Efficacy Analysis Set - Tipping Point Analysis - Multiple Imputation Results | | Statistic | | |
| | | EXPAREL [N=XX] | Placebo [N=XX] | EXPAREL - Placebo |
| N | | xx | xx | |
| Mean | | xxx.x | xxx.x | |
| Standard Deviation | | xxx.xx | xxx.xx | |
| Median | | xxx.x | xxx.x | |
| Minimum | | xx | xx | |
| Maximum | | xxx | xxx | |
| Least squares mean [1] | | xxx.x | xxx.x | xxx.x |
| Least squares standard error of mean [1] | | xxx.xx | xxx.xx | xxx.xx |
| 95% confidence interval for treatment difference [1] | | | | (xxx.x, xxx.x) |
| p-value for treatment difference[1] | | | | 0.xxxx |
| Tipping Point [2] | | | | xx |

Note: AUC = area under the curve calculated using the trapezoidal method;
 NRS = numeric rating scale at rest, where 0 = no pain and 10 = worst possible pain;
 Summary statistics based on the subject mean AUC from the multiple imputations;
 wWOCF + LOCF = imputation using the worst observation prior to use of rescue medication within a medication window and last-observation-carried-forward for missing values.

[1] From an ANOVA with main effects of treatment and site.

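### The MMRM presented as a sensitivity analysis of AUC(0.25-48) reports a different quantity, chosen by an interaction pre-test, in a table labelled as AUC

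*SAP*

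**What the plan says.** SAP sections 7.6.1.1 and 7.6.1.5 define the primary endpoint as AUC(0.25-48), derived by the trapezoidal rule from rescue-adjusted NRS scores at actual assessment times. Section 7.6.2.1 analyses it by ANOVA with treatment and site.

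The first sensitivity analysis in section 7.6.2.1 is a mixed model for repeated measures (MMRM). It uses the rescue-adjusted data, "not imputing any missing values outside of the rescue medication windows", with fixed effects for treatment and time. Site is not in the model, and no covariance structure or set of visits is named. The treatment-by-time interaction is tested first, which gives three branches:

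- Not significant: "If this interaction is not significant (p-value > 0.05) the final model will include the main effects only".
- Significant and quantitative: the interaction stays in the model.
- Significant and qualitative: "If the interaction is qualitative, additional analyses may be required".

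The output is then fixed: "The treatment effect at 48 hours will be estimated from the final model".

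The topline list in SAP section 5 includes "14.2-1.1.3: Sensitivity Analysis of AUC of NRS Pain Intensity Scores through 48 hours". The programmer note under the shell for Table 14.2-1.1.1 has that shell reused for this table. Its footnotes say "From an ANOVA with main effects of treatment and site" and describe "last-observation-carried-forward for missing values".

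**The concern.** A sensitivity analysis for missing data should estimate the primary quantity while changing the missing-data method. This one also changes the quantity. A disagreement with the primary result could come from missing data, or simply from a treatment effect that varies over time, and the second can happen with complete data. Agreement is just as hard to interpret.

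The quantity is also chosen by the data. A non-significant interaction test does not show that the effect is constant, which is what the common effect would need in order to stand in for the AUC difference. The plan cannot assume constancy for a single-dose analgesic followed to 48 hours.

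Finally, the table would show NRS points under an AUC title, with footnotes naming a model and an imputation that were not used. It is expedited after database lock, and it is the only topline sensitivity table on the primary efficacy set.

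**Working it through.** **Plan's own figure.** SAP section 8 states 90% power with 50 per group for an AUC difference of 66 (SD 100) or 86 (SD 130). The standard errors are 100 × √(2/50) = 20 and 130 × √(2/50) = 26. The noncentral t with 98 df gives 90.4% and 90.6%, so the figure reproduces. The plan gives no figure for the MMRM.

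**Response variable.** The SAP does not name it. I take it to be NRS by visit, because the rescue rule acts on individual NRS scores and a single AUC(0.25-48) per subject cannot carry a time effect.

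**Weight of the 48-hour score.** The scheduled times are 0.25, 0.5, 1, 2, 4, 6, 8, 12, 24 and 48 h (protocol section 12.1).

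- The trapezoid weights are 0.125, 0.375, 0.75, 1.5, 2, 2, 3, 8, 18 and 12 h, which sum to 47.75.
- The 48 h share is 12/47.75 = 25.1%. The 24 h share is 18/47.75 = 37.7%, and the eight visits through 12 h share 17.75/47.75 = 37.2%.
- With the SAP section 5 windows, the 48 h share runs from [(46 − 25)/2]/(46 − 0.25) = 10.5/45.75 = 23.0% to [(50 − 23)/2]/(50 − 0.25) = 13.5/49.75 = 27.1%.

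**Weights in the common effect.** In a main-effects model the visit weights depend on the covariance. Compound symmetry gives each of the ten visits 10%. AR(1) of 0.8 by visit order gives 66.7% through 12 h, 5.6% at 24 h and 27.8% at 48 h. Neither matches the AUC weights.

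**Assumptions for the size.**

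- Data are complete and only visits to 48 h enter the model.
- AUC SD is 100 to 128 (the SAP section 8 range), with 50/50 or 100/50 subjects.
- Correlation is compound symmetry 0.4 or 0.6, or AR(1) 0.8. Visit SD is scaled to match the AUC SD, giving 2.5 to 3.6.
- Primary and 48 h power come from the noncentral t without site. Interaction power comes from a 9-df profile test. Joint rates come from 4,000 simulated trials per setting.
- The two effect profiles are illustrations; the documents give none.

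**AUC differences.**

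- Profile 1 (2 points through 12 h, 1 at 24 h, 0 at 48 h): 2 × 17.75 + 1 × 18 + 0 × 12 = 53.5.
- Profile 2 (2 points through 12 h, 1.5 at 24 h, 1 at 48 h): 2 × 17.75 + 1.5 × 18 + 1 × 12 = 74.5.

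The standard error of the AUC difference runs from 100 × √(1/100 + 1/50) = 17.3 to 128 × √(2/50) = 25.6.

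| | Profile 1 | Profile 2 |
|---|---|---|
| AUC difference | 53.5 | 74.5 |
| Primary power | 54–87% | 82–99% |
| True 48 h effect (points) | 0 | 1.0 |
| Power of the 48 h test | 5% (no true effect) | 28–64% |
| Interaction significant | 65–100% | 17–70% |
| Among significant primary results: interaction significant, 48 h not | 59–97% | about 14–32% |

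In profile 1, 19–43% of the trials with a significant primary result also have a significant interaction and a 48 h estimate of the opposite sign. Those could be read as qualitative, the branch with no defined output.

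In profile 2 both reporting branches are common, and they give different answers:

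- Interaction kept: 1.0 point, or 1.0 × 47.75 = 47.8 in AUC units.
- Interaction dropped, compound symmetry: (8 × 2 + 1.5 + 1)/10 = 1.85 points, or 88.3.
- Interaction dropped, AR(1): 2 × 0.667 + 1.5 × 0.056 + 1 × 0.278 = 1.69 points, or 80.9.

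The true AUC difference of 74.5 lies between the two branches and is reported by neither.

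**Constant effect.** With 66/47.75 = 1.38 points at every visit, all the quantities agree up to the factor 47.75, and the discordance rate falls to about 1–2%.

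**The case against.** - **The response is inferred.** The SAP also derives AUCs to 24, 72 and 96 h, so cumulative AUC by horizon could be the repeated measure, and its effect at 48 h would then be the AUC(0.25-48) difference. This reading is strained: the rescue rule acts on NRS scores, and a main-effects branch makes no sense for cumulative AUCs, which grow with the horizon. The response should still be named.
- **The size depends on the profile.** This stands. The rate runs from about 1% with a constant effect to 97% when the effect has gone by 48 h. Nothing in the documents supports an effect of exactly zero at 48 h, and the product is described as releasing drug over an extended period.
- **The 100/50 split is a whole-study figure.** The table uses Amendment 2 subjects only, for whom protocol section 15.3 promises at least 50 per arm. This affects the upper ends of several ranges; the lower ends of the power ranges come from 50/50.
- **The LOCF footnote is boilerplate.** True. It also appears on the primary multiple-imputation table and other shells, where it is equally wrong.
- **Other outputs help.** The tipping-point and wWOCF+LOCF analyses stay on the AUC scale, and NRS by timepoint is tabulated and plotted. A reader could suspect a waning effect, but could not separate its contribution from that of missing data.
- **The corrected MMRM adds little robustness.** It would rest on nearly the same missing-at-random assumption as the primary imputation. This limits what the fix gains; it does not justify reporting another quantity under the AUC title.

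**Conclusion.** The concern holds. Followed exactly, the plan fills a table titled as an AUC analysis with a quantity that is not the AUC difference, selected by a pre-test, footnoted with the wrong model, and undefined in one branch. The branching, the table title and footnotes, and the 25.1% weight come directly from the documents, given that the response is NRS by visit. The discordance rates rest on assumed effect profiles and correlations and should be read as ranges: about 59–97% if the effect has gone by 48 h, about 14–32% if it halves, and about 1–2% if it is constant. The primary test and its error rate are unaffected. The change should be made, but the primary conclusion does not depend on it.

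**What to change.** In SAP section 7.6.2.1, name NRS by scheduled visit from 0.25 to 48 h as the response and state the covariance structure. Always keep treatment-by-time, and delete the interaction pre-test with its quantitative and qualitative branches. Report one estimate in AUC units: the linear contrast of the treatment differences by visit, with weights 0.125, 0.375, 0.75, 1.5, 2, 2, 3, 8, 18 and 12. State that these nominal-time weights approximate the actual-time AUC of section 7.6.1.5. Adding site would align the model with the primary ANOVA, but is secondary.

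Give Table 14.2-1.1.3 its own footnotes, describing the MMRM with no imputation outside rescue windows. Remove the LOCF note from the multiple-imputation shells at the same time.

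The cost is one ESTIMATE statement, one paragraph of SAP text and two footnotes on this table, plus the same note on the other shells. No data collection or subjects are affected.

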13.1.1. Pain Intensity Assessments

Pain intensity will be assessed using the NRS (see [Appendix 1](#)). To assess pain intensity, the subject will assume a resting position that does not exacerbate his or her postsurgical pain. The subject will rest in this position for at least 5 minutes before responding to the following question, *“On a scale of 0 to 10, where 0 = no pain and 10 = worst possible pain, how much pain are you having right now?”* The subject’s response will be recorded.

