7.1.1. Handling Missing Values

7.1.1.1. Area Under the NRS-Time Curve

7.1.1.1.1. Multiple Imputation Method

Rubin’s (1987)⁴ multiple imputation procedure will be applied to replace each missing value with a set of plausible values that represent the uncertainty about the right value to impute. This multiple imputation method is being implemented per the advice provided in “the prevention and treatment of missing data in clinical trials”⁵ For calculation of area under the curve (AUC) of NRS pain intensity scores, the windowed worst observation carried forward (wWOCF) multiple imputation procedure will be used in the following order:

- Windowed worst observation carried forward (wWOCF) for rescue medications.

For subjects who take a rescue medication, their NRS scores recorded within the window of controlled type of rescue medication (see [Table 2](#)) will be replaced by the ‘worst’ observation. The worst observation will be the highest score from time 0.25 or end of previous rescue window, to

pain score immediately prior to rescue medication for those subjects with pain score prior to each rescue medication (Amendment 2) or, for those subjects with pain scores only prior to first rescue medication use (Amendment 1) in the time interval from time 0.25 to up to the time of rescue medication. The NRS score at rescue will be included in this

calculation. Note that NRS scores in the window that are higher than the worst value prior to rescue medication will not be overwritten.

- b) After the wWOCF imputation, described in Step a, subject data still missing with a non-monotone missing pattern (ie, all pain scores between the last non-missing score and last timepoint) will have missing scores imputed using the Markov-Chain Monte-Carlo (MCMC) method (Schafer 1997)⁶, which will be applied in the multiple imputation procedure for arbitrary missing patterns. This MCMC method will use 1000 imputation datasets with NBITER=2000 and NITER=1000.
- c) The resulting data from Step b will then have the remaining monotone missing patterns, hence a parametric regression method on pain (Rubin 1987) that assumes multivariate normality will be applied for this multiple imputation procedure.
- d) The AUC and SPIS at various time intervals will be derived from the imputed NRS scores resulting from Step c.
- e) The endpoints derived in Step d will be analyzed as described in Section 7.6.2.1 for each imputation.

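### The tipping-point shifts are not held to the 0-10 pain scale, so the reported tipping value may rest on scores no subject can give

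*SAP*

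**What the plan says.** Protocol 13.1.1 defines the pain score as "On a scale of 0 to 10, where 0 = no pain and 10 = worst possible pain". The primary endpoint is the AUC of these scores from 0.25 to 48 h.

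If the primary result is significant, the Tipping Point part of SAP 7.6.2.1 says that "the above code will be run iteratively for integer values of Q from 1 to 10 analyzing each step of the way", stopping when significance is lost. Otherwise "the above code will be run iteratively for integer values from -1 to -10 until the result" tips, described as a move "from not clinically significant to clinically significant".

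The shift is coded by time point, in the form "MNAR ADJUST(T1 / SHIFT=Q ADJUSTOBS=(TREATMENT='EXPAREL" and so on, so only the EXPAREL arm moves. The input is set by "PROC MI DATA=OUTDATA_STEPB OUT=OUTDATA_TIP", the output of step b in SAP 7.1.1.1.1. Rescue-window replacements and gaps already filled by MCMC are therefore fixed, and only the remaining monotone gaps are shifted. Those gaps are filled by a regression method "that assumes multivariate normality will be applied for this multiple imputation procedure".

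No minimum, maximum, rounding or truncation appears in SAP 7.1.1.1.1, in the tipping code, or in the example program in SAP Section 12. Table 14.2-1.1.4 reports the tipping value with no criterion for judging its plausibility.

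**The concern.** A shift of up to 10 points on an 11-point scale takes most imputed scores off the scale well before the loop ends. An imputed 4 becomes 14 at Q = 10 and -6 at Q = -10, and these values go straight into the AUC. A reader given only the tipping Q cannot tell whether the result turned on severe but possible pain or on pain of 13 out of 10.

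What is at stake is how a sensitivity analysis is read. If a significant result loses significance only on impossible scores, the report will show a tipping point where no set of possible values for the shifted scores would have produced one. In the negative branch, the same lack of a bound can make a failed result look closer to success than it could be.

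**Working it through.** **Inputs from the documents.** NRS times up to 48 h are 0.25, 0.5, 1, 2, 4, 6, 8, 12, 24 and 48 h (Protocol 12.1). The design values are difference 66, SD 100, 50 per group, two-sided 0.05 and 90% power (SAP Section 8).

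**Assumptions, because the documents are silent.** A fraction p of EXPAREL subjects have no score after 12 h; their mean imputed score is 4; each missing score moves by exactly Q. The SAP does not say whether shifted values feed later regressions and so compound.

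**The plan's own figure.** A two-group t-test with 50 per group, difference 66 and SD 100 has power 0.904 (noncentral t). For 86 and 130 it is 0.906. The stated 90% is reproduced.

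**Margin to non-significance.** SE = 100 × √(2/50) = 20. The critical difference is 1.984 × 20 = 39.7. The margin is 66 − 39.7 = 26.3 AUC units.

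**Weight of the missing times.** By the trapezoidal rule, 24 h carries (12 + 24)/2 = 18 h and 48 h carries 24/2 = 12 h, together 30 h.

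**Effect of Q = 10 per subject.** Unbounded: 10 × 30 = 300 units. Bounded: at most (10 − 4) × 30 = 180 units.

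**Effect on the EXPAREL mean.**

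| p | Unbounded | Bounded (at most) | Margin |
|---|---|---|---|
| 5% | 15 | 9 | 26.3 |
| 10% | 30 | 18 | 26.3 |

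At 10% the unbounded run tips at Q = 26.3/(0.10 × 30) = 8.8, so Q = 9; the bounded run never tips. At 5% neither tips.

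**Allowing for the added spread.** Moving a fraction p by d adds p(1 − p)d² to the EXPAREL variance.
- p = 10%, unbounded: 0.09 × 300² = 8,100. The critical difference becomes 1.984 × √((18,100 + 10,000)/50) = 47.0, and the difference left is 66 − 30 = 36. It tips.
- p = 10%, bounded: 0.09 × 180² = 2,916. The critical difference is 1.984 × √((12,916 + 10,000)/50) = 42.5, and 66 − 18 = 48 is left. It does not tip.
- p = 5%, unbounded: 0.0475 × 300² = 4,275. The critical difference is 1.984 × √((14,275 + 10,000)/50) = 43.7, and 66 − 15 = 51 is left. It does not tip.

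With 100 and 75 subjects, the whole planned enrolment, the unbounded 10% case is borderline: 36.0 against 36.5, using the pooled variance.

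**Share of impossible scores.** With imputed mean 5 and SD 2.5 (assumed), the share above 10 is 50% at Q = 5, 66% at Q = 6 and 98% at Q = 10.

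**Simulation.** Scenarios had 50 per arm, 6% to 20% of EXPAREL subjects with no score after 2 h or 12 h, several assumed pain levels, and about 130 significant trials each. Between 2% and 66% of significant trials tipped only because there was no bound. On average 13% to 77% of shifted scores exceeded 10 at the tipping Q. With 6% missing after 12 h, 22% to 28% tipped only without the bound. These trials include observed differences nearer the significance boundary than 66. No trial survived unbounded Q = 10 and then failed with every shifted score set to 10.

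**The case against.** The strongest reply is that the omission is conservative. In the positive branch it can only make EXPAREL look more fragile. In the negative branch the primary test has already failed. Q itself is reported, so a reader can see that 8 or 9 is extreme on this scale. Subjects stay in the facility for 96 hours (Protocol 13.1), so monotone gaps before 48 h may be few. All of this stands and limits the point to interpretation. But seeing a large Q does not tell the reader whether the result would also have tipped on possible scores.

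A reader might infer that the analysis never reaches the true worst case. The missing bound does not cause that: unbounded Q = 10 puts every non-negative imputed score it shifts at 10 or above, so a result that survives it also covers the case with all of them at 10. Coverage is limited for other reasons. MCMC-filled EXPAREL gaps and placebo imputations are never shifted, and truncation would not change that.

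Nor is this the SAP's main evidence on missing data. SAP 7.6.2.1 also plans an MMRM and a wWOCF + LOCF analysis, and the topline list in SAP Section 5 includes the MMRM table but not the tipping-point table.

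The phrase "from not clinically significant to clinically significant" might be read as an undefined stopping threshold. The same sentence starts from statistical non-significance, and the footnote to Table 14.2-1.1.4 defines tipping by statistical significance, so it is a wording slip.

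Truncating only the shifted runs would also mean that Q = 0 no longer reproduces the primary analysis, whose imputation is itself unbounded. That is correct, and the fix has to allow for it.

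**Conclusion.** The point holds as a cheap improvement to a sensitivity analysis. Shifted scores are not bounded to 0-10, so a reported tipping Q may rest on impossible values and overstate fragility.

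At the planned difference of 66 with 50 per arm, the bound changes the conclusion at 10% missing after 12 h (30 against at most 18 units, margin 26.3) and not at about 5%. A significant trial with a smaller observed difference has a smaller margin, so there the bound can matter at lower rates. The size depends on the assumed missing-data rate and the imputed mean of 4. The group size also matters: 50 per arm is the minimum that Protocol 15.3 seeks under Amendment 2, the population of the primary efficacy set. The primary test and its error rate are unaffected.

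**What to change.** Keep the planned run and report a bounded version beside it:

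- After each shift, set values above 10 to 10 and below 0 to 0 before deriving the AUC.
- Include a truncated Q = 0 run as the reference, so that the effect of clipping is separated from the effect of the shift.
- Report the share of imputed scores truncated at the tipping Q.
- As an editorial correction, align the wording of the negative-Q branch with the statistical significance named in the footnote to Table 14.2-1.1.4.

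The cost is a few lines of code and a second set of tipping runs. For truncated scores the effective shift is less than Q, which the reported share discloses.
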